At the end of this 30 minutes, if the participant would like to complete the first set of questionnaires while he/she is in clinic, he/she will answer the questions on a tablet (or paper if the patient prefers) about his/her quality of life, pain and bladder management. These questionnaires should take about 10 minutes to complete. If the participant does not have the time at the current clinic visit to complete these questions, a link will be emailed to the participant, which when clicked, will take the participant to the Assessment Center, where the questionnaires will be completed. For participants who don't have a computer, who are not able to use a computer or prefer to have the questions read to them, study personnel will set up a time to call and the questions will be completed over the phone.

The patient will be asked to complete the same questionnaires that were completed at baseline, every 3 months for up to 1 year. This will be accomplished by either 1) sending the participant the questionnaire link via email 2) calling the participant and completing the questionnaire via phone 3) approaching the participant at his/her next standard of care clinic visit (if this visit falls within the 3 month window) to see if he/she would like to complete the next set of questionnaires either by paper or table. Also, there is an Exit Interview that will be given when the participant finishes the study. This Exit Interview can be sent to the participant via email with a link to the questions, or the participant can do the Exit Interview over the phone with study personnel; whichever method the participant prefers. The Exit Interview asks questions about any changes over the past year in bladder management, any surgeries that might have affected bladder management and any complications that resulted in a change of bladder management for the participants. The Exit Interview questions will take approximately 15 to 20 minutes to complete.

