our primary analysis for aims 1-3 is to summarize patient experiences over the 12month period, defined by his/her treatment at enrollment (i.e., ignoring any changes in treatment). A secondary analysis for aims 1-3 will be to allow treatment group to be time varying for the 10-15% who are expected to change treatment during the course of the study. This latter type of analysis provides a more general characterization of QoL by treatment type, but it is limited in that it is more difficult to adjust for covariates -- more details are provided below.

Primary Analysis for Aims 1-2:

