
Secondary and Additional Analyses for Aims 1-2:

As a secondary analysis, we will allow treatment group to be a time-varying predictor given that patients can change treatment during the course of the study. This analysis will characterize the average relationship between treatment type and QoL. The key covariates will be the same as for the main analysis, except that we will not consider the interaction between treatment group and time on treatment at baseline, since it is no longer sensible in the context of a changing treatment group (given that time on treatment at baseline corresponds to one particular treatment).

It is also interesting to study patients who switch treatments during the 12m follow-up period. We will investigate potential predictors of switching treatment groups in an exploratory fashion, by modeling treatment change (yes/no) as an outcome and baseline treatment group as a main predictor. This will allow us to evaluate whether the rates of change during the 12 month follow-up period vary by baseline treatment group. Other potential predictors of treatment change will include time on baseline treatment, time since injury, injury severity, patient age, sex and BMI.

Finally, we will repeat the primary analysis model for each of the subscales of the two surveys (using treatment type at baseline as a primary predictor). For the subscale analyses we will plan to report the marginal coefficients, 95% confidence intervals CIs and p-values for each treatment group contrast (3 pair-wise comparisons), and statistical significance will be evaluated at the 0.017 level.

Analysis Plan for Aim 3

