For our tertiary aim of evaluating cumulative complication rates (categorized as 0, 1-3, 3-5, >5) by treatment group on QoL, we will adopt a similar modeling framework as described for Aims 1-2, except that complications will be included in the model along with its interaction with treatment group. We will use a likelihood ratio test to evaluate the statistical significance of this interaction term, i.e. to answer our main question of whether or not the relationship between cumulative complications and QoL differs by treatment group. We will also provide average QoL estimates and 95% CIs for combinations of subcategories of complications, treatment group, treatment duration, time since injury, and age using Stata's margins command. We will also plan to implement the Aims 1-2 secondary analysis where treatment group is modeled as a time varying predictor. Again these models will include the additional interaction term between treatment group and cumulative complications.

While our original analysis for our PCORI grant funding specified data collection for 12 months follow-up, any additional longitudinal data follow-up would be useful and novel data for the field and will be collected as available.

A Note on Missing Data

One benefit of the mixed effects modeling framework is that our models will include all available patients even if a patient has a missing value for one or more time points. However, missing data is likely, and we will plan to use multiple imputation (MI) to investigate the sensitivity of our results to missing data (36, 37).

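### The exploratory switching analysis uses a yes/no outcome that ignores how long each patient was observed, so unequal dropout can create a false difference between baseline groups

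*Combined protocol and SAP*

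**What the plan says.** Under Secondary and Additional Analyses for Aims 1-2, the plan turns to patients who change method during follow-up: "We will investigate potential predictors of switching treatment groups in an exploratory fashion". It will do this "by modeling treatment change (yes/no) as an outcome and baseline treatment group as a main predictor", so as to "evaluate whether the rates of change during the 12 month follow-up period vary by baseline treatment group". The remaining candidates are listed: "Other potential predictors of treatment change will include time on baseline treatment, time since injury, injury severity, patient age, sex and BMI". None of them measures how long a patient was observed. No offset, censoring rule or time-to-event model is given for this analysis, and no rule for a patient lost before 12 months. The quality-of-life models, by contrast, do include the follow-up time point.

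The Analysis Plan Overview refers to "the 10-15% who are expected to change treatment during the course of the study", with no breakdown by group. Under Procedures, questionnaires are repeated "every 3 months for up to 1 year", and "there is an Exit Interview that will be given when the participant finishes the study". That interview asks about changes of bladder management over the past year. The note on missing data says "missing data is likely". It offers mixed models on all available visits, with multiple imputation as a sensitivity analysis, and does not mention switching status.

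**The concern.** A rate over 12 months needs 12 months of observation, or an allowance for less. A patient last contacted at 3 months has had far less chance to be seen switching than one followed for the full year. A single yes/no per patient forces a choice about the first patient, and the plan does not make it. Some of the possible choices turn a difference in dropout into an apparent difference in switching, in either direction.

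At stake is a descriptive finding that readers may take at face value, namely that patients on one method abandon it more often than patients on another. Nothing confirmatory depends on it.

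**Working it through.** The plan has no figure to reproduce here: it gives no sample size, power or event calculation for the switching analysis.

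**Inputs**
- True 12-month switching p = 12.5% in both groups. This is the midpoint of the plan's 10-15%; equality between groups is assumed so that any difference found is false.
- Contacts every 3 months to 12 months, from Procedures.
- Dropout d: not stated in the documents. Assumed 10% in one group against 20%, 30% or 40% in the other, and unrelated to switching.
- Constant switching hazard; lost patients have last contact at 0, 3, 6 or 9 months with equal probability (assumed).

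**Risk seen by last contact in lost patients.** Risk by month t = 1 − 0.875^(t/12): 0%, 3.28%, 6.46% and 9.53% at 0, 3, 6 and 9 months. The mean is m = (0 + 3.28 + 6.46 + 9.53)/4 = 4.82%.

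**Rule A: switches seen up to last contact, lost patients otherwise counted as no.** Observed risk = (1 − d)p + d·m.
- d = 10%: 0.9 × 12.5 + 0.1 × 4.82 = 11.73%
- d = 20%: 10.00 + 0.96 = 10.96%
- d = 30%: 8.75 + 1.45 = 10.20%
- d = 40%: 7.50 + 1.93 = 9.43%

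**Rule B: switches known only from the Exit Interview, lost patients counted as no.** Observed risk = p(1 − d): 11.25%, 10.00%, 8.75%, 7.50%.

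**Rule C: early switchers kept, other lost patients excluded.** Observed risk = [(1 − d)p + d·m] / [(1 − d) + d·m]. For d = 10%: 11.73/(90 + 0.48) = 12.97%. The other three are 13.54%, 14.27% and 15.22%.

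**Rule D: 12-month completers only.** Observed risk = p = 12.5% in every group.

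False odds ratio, lower-dropout group against higher-dropout group (true value 1):

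| Dropout | A | B | C | D |
|---|---|---|---|---|
| 10% vs 20% | 1.08 | 1.14 | 0.95 | 1.00 |
| 10% vs 30% | 1.17 | 1.32 | 0.89 | 1.00 |
| 10% vs 40% | 1.28 | 1.56 | 0.83 | 1.00 |

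Example, rule A, 10% vs 40%: (0.1173/0.8827)/(0.0943/0.9057) = 1.28. With true switching of 10% or 15% instead, the rule A odds ratios stay at about 1.08, 1.17 and 1.27-1.28.

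**Chance of a false positive.** A separate check let dropout happen continuously over the year. Under rule A it gives slightly smaller bias: 11.9% vs 10.6% at 10% vs 30% dropout. The documents state two totals, 1,500 and 4,200-4,400. Equal thirds (assumed) give 1,500/3 = 500 or 4,200/3 = 1,400 per group. Rejection rates of a two-sided 5% test, 500 / 1,400 per group:
- Rule A: 6% / 8% at 10% vs 20%; 10% / 20% at 10% vs 30%; 18% / 41% at 10% vs 40%.
- Rule B: 10% / 19%; 26% / 60%; 53% / 93%.
- Completers only (simulated at 10% vs 30% and 40%): about 5%.

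**After accounting for follow-up time.** In the discrete setting, the risk per 3-month interval among patients still observed is 1 − 0.875^(1/4) = 3.28% in both groups whatever the dropout, and four intervals return 1 − (1 − 0.0328)^4 = 12.5%. In simulation with continuous dropout, person-time rates gave about 12.5% in both groups and false positives of 4.6-5.5%.

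**The case against.** The strongest reply is that the bias depends on a rule the plan has not stated. With a fixed 12-month window a yes/no outcome is a legitimate summary, and rule D shows no bias when dropout is unrelated to switching. That stands. A reader might infer that the planned comparison is necessarily confounded with dropout; the documents do not support this, because they neither choose a handling rule nor report dropout. But they do not choose the completers rule either, and that rule discards partial follow-up.

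The size is also open. Nothing in the documents says dropout differs by method, and a 10-point gap does little under rule A.

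A reader might infer that switches are recorded only at the Exit Interview and that early leavers never receive it. The documents do not say so. The quarterly questionnaires touch on bladder management, their items are not reproduced, and the planned time-varying analysis presupposes method by visit. Rule B is therefore a worse case, not the expected one.

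A further tempting inference is that the time-varying analysis loses the switches of patients who leave. A patient who has left contributes no later scores, so a switch after leaving does not affect that model. Only an unrecorded switch before leaving would matter, by assigning attended visits to the wrong method.

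Multiple imputation might be read to cover switching status, but the plan presents it for the mixed models and does not say so. Finally, the analysis is labelled exploratory, which limits the weight of the point.

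**Conclusion.** The point holds in a limited form. The switching model takes no account of length of observation, and under two plausible handling rules (lost patients counted as non-switchers, or excluded while early switchers are kept) unequal dropout can by itself create a difference between groups, in opposite directions. Under rule A the illustrated false odds ratio runs from about 1.08 to 1.28 for dropout gaps of 10 to 30 percentage points, and it is larger if only the Exit Interview captures switches. These figures rest on assumed dropout rates, a constant switching hazard, and dropout unrelated to switching. The primary quality-of-life contrasts, which use treatment at enrollment and ignore switching, are untouched. This is a cheap improvement to an exploratory analysis, not a threat to the study's main conclusions.

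**What to change.** Model first switch per 3-month interval with a discrete-time logistic or complementary log-log model. Keep baseline group and the same predictors, add the interval, and let each patient contribute intervals until first switch or last contact. Report dropout by baseline group beside the result. Take the method in use from each 3-monthly contact, which the time-varying analysis also needs, with the Exit Interview as a check. If the yes/no model is kept, state how patients lost before 12 months are classified.

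The cost is slightly more analysis work and possibly one added item per quarterly contact, if current method is not already recorded. The model still assumes that dropout is unrelated to switching given the covariates, and the report should say so.

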Patients will be asked if they would like to participate in the study. If they agree than they will be given a consent and allowed to fully review the consent. The consent will specify when they will be contacted and how they will be contacted during the course of the study. When patients feel they have had enough time to fully review the consent they will be enrolled in the study. This process will be the same for patients consenting over the phone, except that patients will be either emailed or mailed a copy of the consent prior to the review of the consent. For patients that are remote consenting, the consent will be on the study website.

Procedures:

This study is an observational/questionnaire study. Patients will be identified and recruited at the (1) University of Utah, (2) University of Minnesota, (3) University of Michigan and (4) University of Western Ontario, Canada. To be eligible, a patient must have a spinal cord injury and/or neurogenic bladder with urinary issues and be using one of the three bladder management treatments (CIC, IDC or urinary diversion). We plan to use the Neuro-QoL developed for PROMIS, a computerized adaptive test questionnaire to assess overall QoL and the Neurogenic Bladder Symptom Score (NBSS) to capture the impact of urinary specific issues and complications on QoL.

Protocol Summary (ERICA) Page **8** of **13** IRB_00082971 IRB Approval 8/26/2015 Baseline Visit: Patients at this visit will be approached regarding study participation. After providing consent and authorization, the patient will have about a 30 minute interview, with a clinician like a physician, nurse, or physician assistant, or a study coordinator who will obtain the medical history. We will gather the following information for our study: patient name, MRN, address, telephone, and email address. If the patient provides consent over the phone or remotely at our study website, the 30 minute interview will take place over the phone.

The patient will be asked very routine questions about his/her health, medication usage, surgical history, physical exam findings, and specifics related to bladder management, bladder health, and specifics regarding the treatments previously received for treatment of neurogenic bladder.

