Our primary endpoints for aims 1 and 2 are the average of total QoL scores over time (total Neuro-QoL score and total NBSS score, respectively). For our primary analysis, these outcomes will be analyzed in a linear mixed effects regression framework, and our primary predictor variable will be the patient's baseline treatment type. Thus, even if a patient switches treatment during our study, we will ignore this change here and consider any change in OoL to just be part of a patient's typical one year experience starting from treatment X. Given that there are only five time points, it should be feasible to model within patient correlations using an unstructured covariance matrix. In these models we will evaluate the three possible pair-wise contrasts: CIC vs. IDC, CIC vs. Surgery and IDC vs. Surgery for statistical significance at the 0.017 Bonferroni-adjusted significance level. Key covariates that will be included in the aim 1-2 models are: time since injury at baseline (coded as a categorical variable with levels <1 year, 1-5 years, and >5 years), physical limitations severity (mild, moderate severe), time on bladder management strategy recorded at baseline (<6 months, 6m-1.5 years, >1.5 years), age at baseline (coded as <20, 20-30, 30-40, 40-50, >50), sex, follow-up time point and BMI. In addition, we hypothesize that interaction effects exist between treatment group at baseline and time on baseline treatment, time since injury, injury severity and patient age. This is because different treatments may have different complication rates, and longer times on a particular treatment may differ from shorter times on the treatment in terms of QoL. Similarly, patient satisfaction (and thus potentially QoL) with treatment type may vary with patient age, time since injury and injury severity. The possibility of additional pair wise interactions between treatment group and the covariates will be investigated in an exploratory fashion. Stata v.12 software will be used to extract the marginal coefficients, 95% confidence intervals (CIs) and p-values for each treatment group contrast in the presence of these interactions using the "margins" command (http://www.stata.com/stata11/margins.html). To summarize patient outcomes by treatment group, we will provide average QoL estimates and 95% CIs for some combinations of treatment group, treatment duration, time since injury, injury severity and age subcategories. While this corresponds to $3^{5}=243$ possible different subcategory combinations, these descriptive results will be estimated from our model based on the full available sample size. Thus these results will provide a profile of expected outcomes for each treatment group given different combinations of patient and injury characteristics.

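### The exploratory model for predictors of switching leaves out baseline Neuro-QoL and NBSS totals, so it cannot show whether switchers were already doing worse

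*Combined protocol and SAP*

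**What the plan says.** The switching analysis is in the section on secondary and additional analyses for Aims 1-2. It is introduced as follows: "We will investigate potential predictors of switching treatment groups in an exploratory fashion, by modeling treatment change (yes/no) as an outcome". Baseline treatment group is the main predictor, and one stated use is: "This will allow us to evaluate whether the rates of change during the 12 month follow-up period vary by baseline treatment group". The remaining predictors are then given: "Other potential predictors of treatment change will include time on baseline treatment, time since injury, injury severity, patient age, sex and BMI". No patient-reported score and no complication variable is in that list, and no other section adds one.

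The scores would be available. The study procedures name the Neuro-QoL and "the Neurogenic Bladder Symptom Score (NBSS) to capture the impact of urinary specific issues and complications on QoL", and set the schedule: "The patient will be asked to complete the same questionnaires that were completed at baseline, every 3 months for up to 1 year".

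The analysis plan overview makes treatment time-varying in a secondary analysis of Aims 1-3, "for the 10-15% who are expected to change treatment during the course of the study". It adds that covariate adjustment is harder there.

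Two other places bear on why patients might switch. The Exit Interview asks about "any complications that resulted in a change of bladder management for the participants". The primary analysis section justifies its interactions by saying that "patient satisfaction (and thus potentially QoL) with treatment type may vary with patient age, time since injury and injury severity".

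**The concern.** The stated task is to find predictors of switching, yet every listed predictor is a treatment, duration, injury or demographic variable. How patients say they are doing, which is what the study measures, is absent.

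This matters because of the time-varying analyses. There, a patient's scores after a switch count towards the new method. If patients who switch tend to be those already reporting poor quality of life or troublesome bladder symptoms, the scores credited to the new method come partly from a group selected on the outcome. If switching is unrelated to earlier scores, that worry recedes. The switching model is the only planned analysis of who switches, and with the listed predictors it cannot help the reader tell these situations apart.

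**Working it through.** The plan states no sample size, power or event count for this model, so there is no figure to reproduce. There are two checks.

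**1. Is the omission real, and are the scores plausible predictors?**
- The list has seven items counting baseline treatment. None is a score, and no other section supplies one.
- Both instruments are completed at baseline, so no new data are needed.
- Age, time since injury and injury severity are on the switching list. The primary analysis section expects these same three to be related to satisfaction and hence perhaps to quality of life, but quality of life itself is not on the list.
- The one reason for switching that the documents name is complications, through the Exit Interview. Complications are not listed either. The NBSS has a Complications subdomain, so its baseline total partly covers that reason.

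**2. Can the data carry two more terms?**

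Inputs: 10-15% expected to switch (analysis plan overview); 1,500 patients (protocol summary) or 4,200-4,400 (study population, all centers). The coding for the switching model is not stated, so the primary model's categories are assumed, with severity at three levels, age at five and BMI linear.

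Listed model: treatment 2 + time on treatment 2 + time since injury 2 + severity 2 + age 4 + sex 1 + BMI 1 = 14 parameters. Adding two continuous totals gives 14 + 2 = 16.

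Switchers = patients × switching rate. Switchers per parameter = switchers / parameters.

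| Patients | Rate | Switchers | 14 parameters | 16 parameters |
|---|---|---|---|---|
| 1,500 | 10% | 150 | 10.7 | 9.4 |
| 1,500 | 15% | 225 | 16.1 | 14.1 |
| 4,200 | 10% | 420 | 30.0 | 26.2 |
| 4,400 | 15% | 660 | 47.1 | 41.2 |

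Score-by-treatment interactions would add 2 scores × 2 treatment contrasts = 4 parameters, making 20. At 1,500 patients that gives 150/20 = 7.5 to 225/20 = 11.3.

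Approximate power for one baseline score at 1,500 patients, two-sided 0.05, is Φ(√(N·p(1−p)(1−R²))·ln(OR per SD) − 1.96). The odds ratios, and R² with the other covariates from 0 to 0.3, are assumptions:
- OR 1.2: 0.43-0.71
- OR 1.3: 0.72-0.95
- OR 1.5: 0.98 to above 0.99

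Example: N = 1,500, p = 0.10, R² = 0, OR 1.3 gives √135 × 0.262 − 1.96 = 1.09, so power is 0.86.

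Two main effects are affordable at either sample size. The expected number of switchers does not explain leaving them out.

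**The case against.** The strongest case for the plan is that this is an exploratory analysis of potential predictors, and the wording of the list need not be exhaustive. The primary analysis deliberately ignores switching, the overview disclaims causal effects of full treatment histories, and no primary or secondary estimate uses the switching model. All of this stands, and it makes the point minor.

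Three stronger readings are tempting, and the documents do not support them.
- A reader might infer that poor scores are the likeliest reason to switch. No section ranks reasons, and the only one named is complications. Plausible is as far as the documents go.
- A reader might infer that a difference in switching between methods is uninterpretable without the scores. It is not: the listed model answers that question. For patients already on a method, baseline scores may partly result from it, so adjusting for them asks a different question.
- A reader might infer that the time-varying results are biased by a known amount, or that a primary result is threatened. Neither is shown.

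A further objection is that the baseline score may be up to a year old when the patient switches, whereas scores shortly before the switch are more telling. Patients may also enroll when just starting a method, so their baseline scores may reflect earlier management. Both limits stand. They restrict what the added model can show, but do not make it uninformative.

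**Conclusion.** The point holds as a minor, inexpensive improvement. The listed predictors omit two collected and plausible predictors of switching, so the only planned analysis of who switches cannot show whether switchers were already doing worse. The consequence is confined to the interpretation of the time-varying analyses; the size of any distortion there is unknown.

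The feasibility result rests on the 10-15% switching rate, on the primary model's coding carrying over, and on switching status being known for everyone. The plan says missing data are likely, so actual counts may be lower. The interactions are not recommended, because they thin the data at the smaller sample size.

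**What to change.** Keep the listed model unchanged for the total difference in switching by baseline method. Add a second exploratory model with the same predictors plus baseline Neuro-QoL total and baseline NBSS total as main effects, without score-by-treatment interactions.

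Report each score's association in that instrument's own scoring direction. The documents give no direction for the NBSS, so a rule keyed to low scores would be ambiguous. Discuss the time-varying results for Aims 1-3 in light of these associations, read the scores alongside time on treatment at baseline, and say in the report that a null finding for baseline scores does not exclude switching driven by later scores or by complications.

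The cost is a short addition to the analysis plan and one more model fit, with no new data collection.

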The primary and secondary aims of this study are to compare total Neuro-QoL score and total NBSS score, respectively, across three common bladder treatments: CIC vs. IDC vs. Urinary diversion/bladder augmentation. While the total scores are our primary outcomes, we will also compare scores for the subdomains of these surveys, which include physical, mental and social function for the Neuro-QoL, and Incontinence, Storage and Voiding Symptoms, Complications, and a QoL item for the NBSS. We will also plan to report subgroup summaries to provide details specific to time since injury and/or treatment duration. The tertiary aim is to investigate whether the relationship between complication rate an effect modifier of the relationship between treatment groups (i.e. is complication rate an effect modifier of the relationship between treatment group and Neuro-QoL). For this aim we will also describe and compare complication rates across bladder treatment groups.

Analysis Plan Overview:

The benefit of this longitudinal design is that it will allow us to capture QoL and complications data on a large cohort for a fairly rare condition. Furthermore, the subjects captured with this design resemble a typical patient population, where subjects present at various times since injury and with varying treatment durations. This is a typical patient population encountered in clinical practice, where the goal is to appropriately council these patients on their treatment options. Because treatment history, outcomes, and covariates are recorded only for a 12-month period and are not available prior to the baseline assessment, it is not possible under our proposed design to evaluate the causal effects of the patients' full bladder treatment histories. Rather, we will characterize the association of the QoL score and other outcomes with the patient's bladder management treatment at enrollment (CIC, IDC or urinary diversion/bladder augmentation) during the 12-month follow-up period for each patient, with adjustment for demographic factors and injury characteristics. Thus the goal for

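### The Aim 3 interaction test uses complication bands with an open top level and no term for the count, so under some conditions it can report effect modification that is not there

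*Combined protocol and SAP*

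**What the plan says.** The Analysis Plan for Aim 3 describes the aim as "evaluating cumulative complication rates (categorized as 0, 1-3, 3-5, >5) by treatment group on QoL". It takes over the Aims 1-2 mixed model and adds the complication bands and their interaction with treatment group. On the test it says: "We will use a likelihood ratio test to evaluate the statistical significance of this interaction term". The question to be answered is "whether or not the relationship between cumulative complications and QoL differs by treatment group". Model-based mean QoL by band and treatment is to be reported with confidence intervals, and the model is to be repeated with time-varying treatment.

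Two other places matter. The Primary Analysis for Aims 1-2 justifies its treatment interactions by noting that "different treatments may have different complication rates". The opening of the statistical section adds: "For this aim we will also describe and compare complication rates across bladder treatment groups".

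The plan gives no analysis of the count as a number, no finer split of the top band, no sensitivity analysis to the banding, and no significance level or power for this test.

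**The concern.** The question is about the relationship between complications and QoL. The test asks whether differences in mean QoL between bands are the same for all three methods. The two coincide only if the counts inside each band are distributed alike across methods, or if QoL does not change with the count inside a band. The closed bands are narrow, so little can go wrong there. The top band has no upper limit. A method with more complications will tend to have a higher mean count inside it, and so a lower mean QoL in that band, even if each complication costs the same on every method. The interaction term absorbs that gap.

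This test is the plan's answer to its main Aim 3 question. If the artefact is present, a rejection cannot be read as complications mattering more on one method. In one direction of true effect, a non-rejection can hide a real difference.

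**Working it through.** **No figure to reproduce.** The documents state no power, effect size or error rate for Aim 3.

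**Inputs from the documents.** Four bands and three groups ("CIC vs. IDC vs. Urinary diversion/bladder augmentation") give (4-1) x (3-1) = 6 df. There are five time points. The background text estimates 1,500 patients; Study Population gives 4,200-4,400 over all centers (4,300 used).

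**Assumed, because the documents are silent.**
- Group mix 50/30/20%.
- Visit SD 1 and within-patient correlation 0.6, so a five-visit patient mean has variance 0.6 + 0.4/5 = 0.68.
- Bands read as 0, 1-3, 4-5, >5.
- Level 5%. The stated 0.017 (0.05/3) is tied to the Aims 1-2 contrasts.
- Counts geometric (negative binomial, shape 1), or less dispersed where noted.
- A patient-level mean and total count stand in for the five-visit model. The plan does not say whether the cumulative count is updated at each visit.

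**Step 1: the top band.** For a geometric count with mean m, E[n | n>5] = 6 + m. This gives 8 at m=2, 10 at m=4 and 14 at m=8. In the 1-3 band the means are only 1.74, 1.85 and 1.92. With a common loss of 0.1 SD per complication and means of 2 and 4, the top band shows a false gap of (10 - 8) x 0.1 = 0.2 SD.

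**Step 2: false rejection when the count-QoL relationship is the same in every group.** Simulated, loss of 0.1 SD per complication, means 2/4/2:

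| Counts or effect shape | N=1,500 | N=4,300 |
|---|---|---|
| Geometric, linear effect | 15-19% | 43-46% |
| Negative binomial shape 2, linear | 8-9% | 16% |
| Poisson, linear | 5% | 6-7% |
| Geometric, effect flat above 8 | 4.7% | 5.5% |
| Geometric, log-shaped effect | 5.5% | 6.9% |

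The first row spans separate simulations; one run of 1,000 replicates gave 14%. At 0.05 SD per complication the geometric case gives 6-7% and 13%.

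A second calculation used noncentral chi-square with residual SD 1. At N=1,500 with geometric counts it gave 5.0% for equal rates. For means 2/4/8 it gave 20.8% at 0.05 SD and 71.2% at 0.10 SD. Simulation with variance 0.68 gave 31% and 85% for the same cases; the smaller residual variance is the main difference. When the effect was made flat above 6, the rate returned to 5.0-5.1%, so the open band causes nearly all of the inflation. Reading a count of 3 either way changes little (20.8% against 21.0%), so repairing the overlap at 3 does not remove the problem.

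**Step 3: masking.** Take slopes of -0.10/-0.05/-0.10. If every group averages 8 in the top band, the true gap there is 0.8 - 0.4 = 0.4 SD. If the mild-slope group averages 10, it is 0.8 - 0.5 = 0.3 SD. At N=1,500 the band test rejects 42% of the time with means 2/2/2 but 33-34% with means 2/4/2. A graded count interaction over a spline main effect goes from 65% to 82%.

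**Step 4: where bands do as well or better (N=1,500).** If the high-rate method has the steeper slope (-0.05/-0.10/-0.05, means 2/4/2), bands reject 89% against 82% for the graded test, partly through the artefact. With equal means of 2 there is no artefact. Bands then reject 62-64% against 35% for an any-versus-none modification, and 64-69% against 6% for one confined to 1-3 complications.

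**Step 5: candidate repairs.**
- Spline main effect for the count, with the band-by-treatment interaction kept: false rejection about 5-7% in every null tried, and no power lost in four alternatives.
- Count plus log(1+count), each crossed with treatment (4 df): false rejection 5.0% in five nulls at means 2/4/8. Power is 68% against 49% for bands (slopes -0.03/-0.05/-0.09, mean 3 in every group), and 43% against 46% for any-versus-none.
- A straight-line count for both main effect and interaction: 30-98% false rejection under common concave or step effects with unequal rates. This is not safe.

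**The case against.** The headline size needs three things together: unequal rates, a heavy-tailed count, and a loss that continues well above 5 complications. A loss of 0.1 SD per complication means a full SD at 10 complications. Remove any one condition and the error is largely gone at means 2/4/2. All of this stands. A reader might infer that the planned test is invalid or that any rejection would be spurious; the documents do not support that, because they give no count distribution, rates or dose-response.

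A reader might also infer that banding simply wastes power. Step 4 shows otherwise: bands do better for threshold or single-band modification, and the plan asks about the relationship in general, not about a slope.

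It can further be said that the plan defines the exposure as bands, so the test matches its own definition. That is formally right. But a band contrast that shifts with the mix of counts inside the band does not answer the question as the plan words it.

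Finally, Aim 3 is tertiary and associational, and rates and band-level means will be shown by group. This limits the stakes. It does not reveal the artefact, because mean counts inside the bands are not promised.

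**Conclusion.** The concern holds in conditional form. The planned test can report effect modification that is not there when rates differ by method, counts are overdispersed and QoL keeps falling above 5 complications. The plan anticipates the first condition and is silent on the other two. Within the assumed scenarios the false-rejection rate runs from about 5% to well above nominal, and where the artefact exists it grows with sample size. It can also mask a real difference when the high-rate method has the milder effect; a general loss of power is not shown. The exact size cannot be settled from the documents. Because the safeguard costs almost nothing, the plan should be changed rather than left to depend on the counts turning out favourable.

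**What to change.** In the Analysis Plan for Aim 3, keep the cumulative complication count as a number and add it to the model as a flexible main effect, for example a restricted cubic spline with knots reaching into the upper tail (0, 2, 4, 7 and 12 were used in the checks). Do this in both the baseline-treatment and the time-varying versions. Base the likelihood ratio test on one of two pre-specified terms:

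- the treatment interaction with the bands, made non-overlapping, on top of that main effect; or
- a flexible count-by-treatment interaction, for example count plus log(1+count), 4 df.

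Do not rest the test on a single linear slope interaction. Keep the bands for the descriptive margins tables.

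The cost is SAP wording, a few more model terms, and storing the count as a number; no new patients or visits. The 4-df version has somewhat less power than bands for any-versus-none modification, and clearly less for modification confined to one band. If those patterns matter most, the first option is the better choice.
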